3.1. Analysis Sets

Analysis sets define the participants to be included in an analysis. Analysis sets and their definitions are provided in this section (and are determined prior to unblinding). The analysis set will be identified and included as a subtitle for each table, figure, and listing.

For each analysis set, the number and percentage of participants eligible for inclusion, will be summarized separately for each population by treatment group (active participants within each cohort followed by all participants [within population] assigned to placebo) and overall for all participants in the population.

A listing of reasons for exclusion from analysis sets will be provided by participant.

3.1.1. All Randomized Analysis Set

All Randomized Analysis Set includes all participants who were randomized into the study (ie, received a study participant ID number in the interactive response technology [IRT]).

All Randomized Analysis Set is the primary analysis set for by-participant listings.

3.1.2. Safety Analysis Set

The Safety Analysis Set includes all participants who received at least 1 dose of study drug.

The Safety Analysis Set is the primary analysis set for safety analyses.

3.1.3. Immunogenicity Analysis Set

The Immunogenicity Analysis Set includes all randomized participants who received at least 1 dose of study drug and have at least 1 value for HBV-specific T-cell total response using the interferon gamma (IFN- γ) enzyme-linked immunospot (EliSpot) assay after administration of the investigational product.

The Immunogenicity Analysis Set will be the primary analysis set for immunogenicity analysis utilizing the IFN- γ EliSpot assay.

3.1.4. Full Analysis Set (Virally Suppressed CHB Participants only)

The Full Analysis Set (FAS) will include all virally suppressed CHB participants who were randomized, and received at least 1 dose of investigational product.

The FAS will be the primary analysis set for efficacy analysis for phase 1b participants.

3.2. Participant Grouping

For analyses using the Immunogenicity Analysis Set (both populations) and analyses in virally suppressed CHB participants only using the FAS, participants will be grouped according to population, treatment group (active group within each cohort followed by all participants [within population] assigned to placebo) to which they were randomized. For all other analyses, participants will be grouped according to population, treatment group (active group within each cohort followed by all participants [within population] assigned to placebo) based on actual treatment received. The actual treatment received will differ from the randomized treatment only when the participant's actual treatment differs from their randomized treatment for the entire treatment duration.

For enrollment, disposition, analysis sets, demographics and baseline characteristics, and baseline disease characteristics [virally suppressed CHB participants only], an additional total column for population (healthy participants or virally suppressed CHB participants) will be included. For all other tables, a population total column will not be presented.

Data will be summarized separately for healthy participants (Phase 1a) and virally suppressed CHB participants (Phase 1b). Within each population, displays will be by “cohort” for participants randomized to/taking active study drug within each cohort plus a pooled “placebo” group for the relevant population. Participants randomized to/taking placebo will be pooled across all cohorts within the population to form a single “placebo” group for summaries.

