8.3.1.2. Safety

The Safety Analysis Set will include all randomized participants who received at least 1 dose of investigational product. Participants who received treatment other than that to which they were assigned will be analyzed according to the treatment received.

The Safety Analysis Set is the primary analysis set for safety analyses. All data collected during the study will be included in the safety summaries.

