8.5. Safety Analysis

All safety data collected on or after the date that investigational product was first administered up to study completion will be summarized by population and treatment group according to the investigational product received. Data for the pretreatment period and up to study completion will be included in data listings.

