2.3. Changes from Protocol-Specified Analysis

No changes from protocol-specified analyses are planned.

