4.2. Extent of Study Drug Exposure

For each participant, the number of injections received for each type of vector (GS-2829 and/or GS-6779) and dose level (high dose or low dose for participants receiving active treatment) or placebo for each vector will be calculated. For each population and treatment group (active participants within each cohort followed by all participants [within population] assigned to placebo), the number of participants taking 0, 1, 2, or 3 doses of the vector and dose level combination or placebo for the vector will be provided. Dosing information will be summarized based on data collected on the Study Drug Administration eCRF. Subjects who took only one of the vectors (eg, GS-2829 in Cohort 1 and GS-6779 in Cohort 2) will have 0, 1, or 2 injections for the vector administered/Low Dose or placebo for the vector. Cohorts 3 to 8 will have the number of injections received (0, 1, 2, or 3) for each of the following categories:

- GS-2829 Low Dose
- GS-2829 High Dose
- GS-2829 Placebo
- GS-6779 Low Dose
- GS-6779 High Dose
- GS-6779 Placebo

A by-participant listing of study drug administration will be provided separately for each participant population. Sort order will be as described in Section 3 of this SAP.

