4.3. Protocol Deviations

Protocol deviations occurring after participants entered the study are documented during routine monitoring. The number and percentage of participants with at least 1 important protocol deviation (IPD) will be summarized by treatment group for the All Randomized Analysis Set. The following subcategories will also be displayed by treatment group:

- Number of IPDs for each participant (1, 2, or 3 or more IPDs)
- Total Number of Important Protocol Deviations
Note: A participant may be counted across multiple important protocol deviation categories.

A by-participant listing will be provided for those participants with protocol deviations. The listing of protocol deviations (IPDs and non-IPDs) will include a column to specify whether the protocol deviation is an IPD.

Participants who did not meet eligibility criteria for study entry but were enrolled will be listed separately for each population.

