7.1.3. Relationship of Adverse Events to Study Drug

Related AEs are those for which the investigator selected “Related” on the AE eCRF to the question of “Related to Study Treatment.” Relatedness will always default to the investigator’s choice, not that of the medical monitor. For this study, relationship is recorded separately for GS-2829/PBO and GS-6779/PBO and for related to any study drug (eg, related to either [or both] of the 2 study drugs). Events for which the investigator did not record relationship to study drug will show the relationship as missing.

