7.1.6.1. Definition of Treatment-Emergent Adverse Events

Treatment-emergent adverse events (TEAEs) are defined as any AE with a start date on or after the study drug start date; or any AE that led to premature discontinuation of study drug.

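### SAP 3.2 would keep a placebo-randomized participant who received some active injections in the pooled placebo column of the safety tables, a narrower rule than the protocol's and not declared (minor)

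*SAP*

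**What the plan says.** Protocol 8.3.1.2 defines the Safety Analysis Set and states: "Participants who received treatment other than that to which they were assigned will be analyzed according to the treatment received". Protocol 8.5 repeats the principle: safety data are "summarized by population and treatment group according to the investigational product received". Neither section sets a duration condition, and neither says what to do with a participant who received both placebo and active vector.

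SAP 3.2 uses randomized treatment for the Immunogenicity and Full Analysis Sets and actual treatment for everything else, including safety. It then lets actual treatment depart from randomized treatment only when the "actual treatment differs from their randomized treatment for the entire treatment duration". Placebo participants are pooled across cohorts within each population. SAP 2.3 states: "No changes from protocol-specified analyses are planned".

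Three other sections bear on the point:

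- SAP 4.2 tabulates "the number of injections received for each type of vector (GS-2829 and/or GS-6779) and dose level", or placebo, and adds an administration listing.
- SAP 4.3 promises: "A by-participant listing will be provided for those participants with protocol deviations".
- SAP 7.1.6.1 treats as treatment-emergent "any AE with a start date on or after the study drug start date", so the clock runs from the first injection of any kind.

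On a separate matter, SAP 7.1.3 says: "Events for which the investigator did not record relationship to study drug will show the relationship as missing". SAP 7.1.7 admits to the drug-related displays only events marked related. SAP 7.1.4 takes the opposite default for procedures and counts a missing relationship as related.

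**The concern.** Each injection is a separate vaccine exposure. In Cohorts 1 and 2 a full course is two injections, so a placebo-randomized participant given one active injection has had half an active course and still counts as placebo. In the six-dose cohorts, five active injections out of six would not move the participant.

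The affected tables carry the primary endpoint: the proportions with treatment-emergent AEs, SAEs and laboratory abnormalities. The placebo columns are small and serve as the reference. An event that follows an active injection would be read there as background. The exposure table would show the stray injection, but the AE and laboratory tables would not.

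**Working it through.** **Inputs.** Eight cohorts of 8 active and 2 placebo (SAP 1.3). Phase 1a comprises Cohorts 1, 2, 3, 4 and 8; Phase 1b comprises Cohorts 5, 6 and 7. Doses per participant are 2 (Cohorts 1–2), 4 (Cohorts 3–6) and 6 (Cohorts 7–8). Last visits are Day 225, 253 and 309.

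**Planned size.** 8 × (8 + 2) = 80, which agrees with the plan: 50 in Phase 1a and 30 in Phase 1b. Pooled placebo is 5 × 2 = 10 and 3 × 2 = 6. Planned placebo injections are 2 × (2+2+4+4+6) = 36 and 2 × (4+4+6) = 28, 64 in all.

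**Effect of moving one participant on the placebo rate.** Let x of n placebo participants have the event.

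- The moved participant had the event: x/n becomes (x−1)/(n−1). The fall is largest at x = 1: 1/10 to 0/9 (10.0 points) or 1/6 to 0/5 (16.7 points).
- The moved participant did not: x/n becomes x/(n−1). For example, 3/6 = 50.0% becomes 3/5 = 60.0%. The rise is largest at x = n−1: 5/6 to 5/5 (16.7 points), or 9/10 to 9/9 (10.0 points).

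**Illustration.** Suppose the misdosed participant has the only event.

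| | SAP 3.2 rule: placebo, active cohort | Any active dose counts: placebo, active cohort |
|---|---|---|
| Phase 1a | 1/10 (10.0%), 0/8 (0%) | 0/9 (0%), 1/9 (11.1%) |
| Phase 1b | 1/6 (16.7%), 0/8 (0%) | 0/5 (0%), 1/9 (11.1%) |

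Active minus placebo goes from −10.0 to +11.1 points, and from −16.7 to +11.1. The exact 95% intervals are wide (1/10: 0.3–44.5%; 1/9: 0.3–48.2%).

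**How likely is an error?** The documents give no rate. At an assumed 0.1% to 0.5% per injection, the chance of at least one error among the 64 placebo injections is 1 − 0.999^64 = 6.2% to 1 − 0.995^64 = 27.4%. This is the chance of an error, not of a changed table.

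**Which column misplaces less?** Take one error at a random dosing visit. The share of planned follow-up before it is (dose day − 1)/last day.

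| Doses | Placebo injections | Mean share before | Error at last dose |
|---|---|---|---|
| 2 | 4 × 2 = 8 | 28/225 = 12.4% | 56/225 = 24.9% |
| 4 | 8 × 4 = 32 | 42/253 = 16.6% | 84/253 = 33.2% |
| 6 | 4 × 6 = 24 | 70/309 = 22.7% | 140/309 = 45.3% |

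Weighted: (8 × 12.4 + 32 × 16.6 + 24 × 22.7)/64 = 18.4% before and 81.6% after. Counted by injection instead, the current rule leaves (8/2 + 32/4 + 24/6)/64 = 25% of such a participant's injections (the active ones) under placebo. The alternative puts the other 75% (placebo injections) under active.

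**Missing relatedness.** One affected participant with no other related AE shifts an active cohort's related-AE rate by up to 1/8 = 12.5 points. In the vector-specific placebo columns, n is 8 per vector in Phase 1a (Cohorts 1, 3, 4, 8 for GS-2829; 2, 3, 4, 8 for GS-6779), so 12.5 points. In Phase 1b n is 6, so 16.7 points.

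**The case against.** A reader might infer that the SAP contradicts the protocol. The documents do not support that. A participant with five placebo injections and one active injection received both, and the protocol does not say which column takes such a person. Protocol Section 8 leaves statistical detail to the SAP, so SAP 3.2 can fairly be read as an operational definition. What stands is that it adds a condition the protocol wording lacks, without saying so in SAP 2.3.

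A reader might also take the sign reversal above as evidence of a biased safety comparison. It is a constructed case with a single event, no dosing error is reported, and the intervals overlap almost entirely. An error would also be visible in the exposure table, the administration listing and the deviation listing. There is no formal test to affect; the cohort stopping rules and the Safety Review Team displays do not depend on this grouping.

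The choice of column is partly a preference. By calendar time the current rule misplaces more; by injection it misplaces less. Neither count settles it, because placebo injections given after an active one are not clean placebo experience. For a first-in-human safety table, keeping the placebo column free of active exposure is the more conservative choice.

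A bare any-active-dose rule would create its own fault. SAP 7.1.7 restricts each vector-specific denominator to active-column participants with an active dose of that vector, and placebo-column participants with its placebo. Someone moved to active after one active GS-2829 injection, with only placebo for GS-6779, would fall out of both GS-6779 denominators. The fix must deal with this.

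On relatedness, the protocol sets no default for a missing value, investigators must judge each product yes or no (Protocol 7.2.1), and queries are resolved before the final analysis. SAP 7.1.7.1 lists no procedure-related table, so the contrast with SAP 7.1.4 carries little weight.

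**Conclusion.** The point holds, and it is minor. If a placebo-randomized participant receives active vector at some but not all visits, SAP 3.2 places events after the active injection in a pooled placebo column of 10 or 6. Reclassifying that participant changes a placebo rate by at most 10.0 or 16.7 points, through the numerator, the denominator or both. These figures assume planned enrolment and full dosing. Whether the situation arises is unknown; the 6–27% rests wholly on an assumed error rate. A wrong assignment held for the whole course is already reclassified correctly.

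The missing-relatedness point is separate and optional. A reader might infer that it weakens the primary endpoint. It does not: those AEs remain in the all-TEAE, grade and SAE tables and drop out only of the drug-related summaries.

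**What to change.** **SAP 3.2, Safety Analysis Set tables only.** Place any placebo-randomized participant who received at least one active injection in the active column of their cohort. Footnote the injections received and any events that began before the first active one.

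**SAP 7.1.7 and 7.1.7.1.** In the vector-specific related-AE displays, classify by what was received for that vector. A participant who received only placebo for a vector then stays in that vector's placebo denominator.

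**SAP 2.3.** Record the rule. If the SAP is already final, document it in the CSR, as SAP Section 1 provides.

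**Optional, SAP 7.1.3.** In summaries, count a missing drug relationship as related for a vector (or its placebo) already received by AE onset, and show it as missing in listings. A blank for a vector not given, or not yet given, is not counted.

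**Cost.** A few sentences and footnotes, with no new data, since injections are already tabulated under SAP 4.2. Because TEAEs run from the first dose, some events that began on placebo move to the active column. A minimally exposed participant also enters the active denominator: 2/8 = 25.0% becomes 2/9 = 22.2% if they had no event, or 3/9 = 33.3% if they did. The optional change may raise related-AE counts slightly, and needs the incomplete-date rule in SAP 7.1.6.2 extended to each vector's first dose.

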8.5.2. Adverse Events

The analysis of data on safety and reactogenicity events will be based on the Safety Analysis Set. Data from participants receiving PBO in different cohorts may be combined within the same population for the final analysis.

Clinical and laboratory AEs will be coded using the current version of the MedDRA. System organ class, high-level group term, high-level term, preferred term (PT), and lower-level term will be attached to the clinical database.

Events will be summarized on the basis of the date of onset for the event. A treatment-emergent AE will be defined as:

- Any AE that begins on or after the date of first dose of investigational product and through the duration of the study; or any AE leading to investigational product discontinuation.

Summaries (number and percentage of participants) of treatment-emergent AEs (by system organ class, high-level term, if applicable, and PT) will be provided by population and treatment group using the current version of MedDRA.

- All TEAEs
- TEAEs of Grade 3 or higher
- TEAEs of Grade 2 or higher
- All treatment-related TEAEs
- Treatment-related TEAEs of Grade 3 or higher
- Treatment-related TEAEs of Grade 2 or higher
- All treatment-emergent SAEs
- All treatment-related treatment-emergent SAEs
- All TEAEs leading to premature discontinuation of any investigational product
- All TEAEs leading to temporary interruption of any investigational product

All AEs collected during the study will be presented in the data listings.

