3. GENERAL CONSIDERATIONS FOR DATA ANALYSES

Analysis results will be presented separately for the 2 participant populations (healthy participants [phase 1a] and virally suppressed CHB participants [phase 1b]) using descriptive statistics. Summaries will be presented by treatment group (active participants within each cohort followed by all participants [within population] assigned to placebo). For categorical variables, the number and percentage of participants in each category will be presented; for continuous variables, the number of participants (n), mean, standard deviation (SD) or standard error (SE), median, first quartile (Q1), third quartile (Q3), minimum, and maximum will be presented.

By-participant listings will be presented separately for the 2 populations (healthy participants [phase 1a] and virally suppressed CHB participants [phase 1b]) for the All Randomized Analysis Set. Listings will be sorted by cohort and participant identification (ID) number, visit date, and time (if applicable). Data collected on log forms, such as AEs, will be presented in chronological order within the participant. The cohort and treatment group to which participants were initially assigned will be used in the listings. Age, sex at birth, race, and ethnicity will be included in the listings, as space permits.

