7.1.7.1. Summaries of AE Incidence in Combined Severity Grade Subsets

A brief, high-level summary of the number and percentage of participants who experienced at least 1 TEAE in the categories described below will be provided separately for each population by treatment group (active group within each cohort and all participants [within population] assigned to placebo). All deaths observed in the study will also be included in this summary.

- TEAEs
- TEAEs with Grade 3 or Higher
- TEAEs with Grade 2 or Higher
- TEAEs Related to Study Drug
- TEAEs Related to Study Drug with Grade 3 or Higher
- TEAEs Related to Study Drug with Grade 2 or Higher
- TEAEs Related to GS-2829/PBO
- TEAEs Related to GS-2829/PBO with Grade 3 or Higher
- TEAEs Related to GS-2829/PBO with Grade 2 or Higher
- TEAEs Related to GS-6779/PBO
- TEAEs Related to GS-6779/PBO with Grade 3 or Higher
- TEAEs Related to GS-6779/PBO with Grade 2 or Higher
- TE Serious AEs
- TE Serious AEs Related to Study Drug
- TE Serious AEs Related to GS-2829/PBO
- TE Serious AEs Related to GS-6779/PBO
- TEAEs Leading to Premature Discontinuation of Study Drug
- TEAEs Leading to Premature Discontinuation of Study
- Death During the Study

Multiple events will be counted only once per participant in each category.

For the AE categories described below, summaries will be provided separately for each population and will be summarized by treatment group (active group within each cohort and all participants [within population] assigned to placebo), SOC and PT:

- TEAEs by severity
- TEAEs with Grade 3 or Higher, by severity
- TEAEs with Grade 2 or Higher
- TE Treatment-Related AEs, by severity
- TEAEs Related to Each of the Individual Study Drugs
- TE Treatment-Related AEs with Grade 3 or Higher, by severity
- TE Treatment-Related AEs with Grade 2 or Higher
- TE Serious AEs
- TE Treatment-Related Serious AEs
- TEAEs Leading to Interruption of Any Study Drug
- TEAEs Leading to Premature Discontinuation of Any Study Drug

Multiple events will be counted only once per participant in each summary. Adverse events will be summarized first in alphabetic order of SOC, and then by PT in descending order of total frequency for the population within SOC. For summaries by severity grade, the most severe grade will be used for those AEs that occurred more than once in an individual participant during the study.

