7.2.2.1. Treatment-Emergent Laboratory Abnormalities

Treatment-emergent laboratory abnormalities are defined as values that increase at least 1 toxicity grade from baseline at any time postbaseline. If the relevant baseline laboratory value is missing, any abnormality of at least Grade 1 observed postbaseline will be considered treatment emergent.

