7.2.2.2. Summaries of Laboratory Abnormalities

The following summaries (number and percentage of participants) for treatment-emergent laboratory abnormalities will be provided separately for each participant population by treatment group (active group within each cohort and all participants [within population] assigned to placebo) for each lab test. Participants will be categorized according to the most severe postbaseline abnormality grade for a given lab test:

- Graded laboratory abnormalities
- Grade 3 or 4 laboratory abnormalities

For all summaries of laboratory abnormalities, the denominator is the number of participants with ≥ 1 nonmissing postbaseline value for the lab test of interest.

A by-participant listing of treatment-emergent laboratory abnormalities, and Grade 3 or 4 laboratory abnormalities will be provided by participant population, cohort, participant ID, and visit in chronological order. This listing will include all test results that were collected throughout the study for the lab test of interest, with all applicable severity grades and abnormal flags displayed.

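### Primary safety tables count participants once over the whole study beside one mixed-schedule placebo column per population; a per-injection adverse-event table is missing, which matters mainly in Phase 1a and for reading the third dose

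*SAP*

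**What the plan says.** The primary endpoint is the proportion of participants with treatment-emergent adverse events (TEAEs), serious adverse events and laboratory abnormalities (Protocol Section 2, SAP 1.1).

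- **Adverse events.** SAP 7.1.6.1 counts "any AE with a start date on or after the study drug start date". Protocol 8.5.2 has the same open window: "Any AE that begins on or after the date of first dose of investigational product and through the duration of the study". SAP 7.1.7.1 adds: "Multiple events will be counted only once per participant in each category".
- **Laboratory abnormalities.** SAP 7.2.2.1 counts "values that increase at least 1 toxicity grade from baseline at any time postbaseline", and SAP 7.2.2.2 says "Participants will be categorized according to the most severe postbaseline abnormality grade for a given lab test".
- **Columns.** The active arm of each cohort stands beside one placebo column per population. SAP 3.2 states: "Participants randomized to/taking placebo will be pooled across all cohorts within the population to form a single" placebo group. Protocol 8.5.2 permits this pooling but does not require it.
- **Schedules.** Cohorts 1 and 2 have 2 injections and follow-up to Day 225. Cohorts 3 to 6 have 4 injections, to Day 253. Cohorts 7 and 8 have 6 injections, to Day 309 (Protocol Synopsis and Table 8).
- **Exposure.** SAP 4.2 tabulates "the number of participants taking 0, 1, 2, or 3 doses of the vector and dose level combination or placebo for the vector" by treatment group. Listings are sorted by cohort (SAP 3).

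No planned TEAE or graded-laboratory incidence table is per injection, exposure-adjusted or limited to a common window.

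**The concern.** More injections, blood draws and days give more chances to be counted once. A six-injection cohort beside a column averaging fewer injections will tend to show a higher proportion even if the vectors do nothing, and a two-injection cohort a lower one. Part of any gap between active and placebo then reflects schedule, and no planned table separates that part.

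A second limit does not depend on placebo. Cohorts 7 and 8 were added to study a third dose of each vaccine (Protocol 11.9.1). Comparing Cohort 8 with 4, or 7 with 6, on a cumulative count cannot distinguish reactions that worsen at the third dose from reactions that only accumulate.

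**Working it through.** **The plan's own figures.** 8 cohorts × (8 active + 2 placebo) = 80 = 50 + 30. Follow-up after the last dose is 225 − 57 = 253 − 85 = 309 − 141 = 168 days in every cohort, so only the dosing period differs (56, 84 or 140 days). All reproduce. There is no power calculation to check.

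**Placebo columns as planned.** Phase 1a: 4, 4 and 2 participants with 2, 4 and 6 injections, 4×2 + 4×4 + 2×6 = 36 injections. Phase 1b: 4 and 2 participants with 4 and 6 injections, 28 in all. Scheduled postbaseline draws for hematology, chemistry and coagulation number 7, 10 or 14 (SAP Table 3-1). Urinalysis differs (7, 8 or 12) because Cohorts 3 to 8 have none on Days 15 or 43.

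**Injection-driven events, inert vectors.** Let p be the assumed risk per injection and k the number of injections. If injections are independent, P(any) = 1 − (1 − p)^k. With within-person correlation ρ, use a beta-binomial with a = p(1 − ρ)/ρ and b = (1 − p)(1 − ρ)/ρ. The placebo value is the weighted mean over schedules: 0.4/0.4/0.2 in Phase 1a, 4/6 and 2/6 in Phase 1b. Entries are percentages; gaps are in points.

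| p, ρ | k = 2 / 4 / 6 | Placebo 1a | Cohorts 1–2 gap | Cohorts 3–4 gap | Cohort 8 gap | Cohort 7 gap |
|---|---|---|---|---|---|---|
| 2%, 0 | 4.0 / 7.8 / 11.4 | 7.0 | −3.0 | +0.8 | +4.4 | +2.4 |
| 10%, 0 | 19.0 / 34.4 / 46.9 | 30.7 | −11.7 | +3.7 | +16.1 | +8.3 |
| 20%, 0 | 36.0 / 59.0 / 73.8 | 52.8 | −16.8 | +6.3 | +21.0 | +9.8 |
| 10%, 0.6 | 13.6 / 17.3 / 19.4 | 16.2 | −2.6 | +1.0 | +3.2 | +1.4 |
| 20%, 0.6 | 26.4 / 32.6 / 36.1 | 30.8 | −4.4 | +1.8 | +5.3 | +2.3 |

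The Phase 1b placebo value is 38.5% at p = 10% and 64.0% at p = 20% (independent). At p = 90%, independent, the Cohort 8 gap is +0.4.

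**Time-driven events.** P(any) = 1 − exp(−λd/365.25), with d = 225, 253 or 309 days. At λ = 1 per year this gives 46.0, 50.0 and 57.1% against a Phase 1a pool of 49.8%, so Cohort 8 is at +7.3. Over all λ the Cohort 8 gap peaks at about +7.6, Cohorts 1–2 reach about −4 and Cohort 7 stays under +5.

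**Blood-test limb.** The same formulas with k = 7, 10, 14 and 1–5% per draw give Cohort 8 gaps of +4.0 to +12.9 if draws are independent and +0.3 to +1.2 at ρ = 0.6.

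**Scale against chance.** For independent injections, the standard error of Cohort 8 (n = 8) minus placebo (n = 10), keeping placebo schedules separate, is √[q₆(1 − q₆)/8 + Σnₖqₖ(1 − qₖ)/10²], where qₖ = P(any) and nₖ is the placebo number with k injections. It is 22.6 points at p = 10% and 21.7 at 20%. From exact distributions, Cohort 8 shows a higher proportion than placebo with probability 0.73 and a lower one with 0.24 at p = 10%, independent. At ρ = 0.6 these are 0.58 and 0.39. For Cohort 7 at p = 10%, ρ = 0.6, they are 0.485 and 0.459.

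**Vector-specific related rows.** SAP 7.1.7 limits the denominator to participants given that vector or its placebo. In Phase 1a that mixes 2, 2, 2 and 3 doses (mean 2.25), so the tilt is reduced but not removed.

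**Per-injection form.** Events divided by injections given has expectation p in every column if p is constant across injections, so the schedule gap is 0 at any ρ. A common calendar window does not achieve this: through Day 112, Cohorts 1–2 have 2 injections and Cohorts 3–8 have 4.

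**The case against.** The other side has a strong case. The analysis is descriptive, with no testing (SAP 3.5). The planned Safety Review Team displays are by population and cohort (SAP 2.1.1). The protocol permits pooling, and unpooling leaves two placebo participants per cohort. The exposure table and listings let a reader rebuild a matched view for about 80 people. The largest tilt is smaller than one standard error, and the +16 to +21 points require every event to be injection-triggered and independent within person.

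All of that stands, and it limits the point to how the tables are read. It does not remove it: the exposure table links no injection to an event, the listings would have to be re-tabulated by hand, and the tilt is systematic where chance is not.

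A reader might go further and infer that pooling distorts dose-escalation decisions, that Cohort 7 is affected as much as Cohort 8, or that the plan ignores exposure. The documents support none of these. The planned review displays are by cohort, the Phase 1b column mixes only 4 and 6 injections, and SAP 4.2 reports injections received, including placebo.

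**Conclusion.** The point holds as a cheap improvement to the descriptive safety tables. In Phase 1a, schedule alone tends to put Cohort 8 above the placebo column and Cohorts 1–2 below it, while Cohorts 3–4 sit close to it. In Phase 1b the Cohort 7 tilt is small, and at correlation 0.6 its direction is close to a coin toss.

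The sizes rest on assumed rates, equal risk in active and placebo, and the planned 8:2 allocation. They fall sharply with within-person correlation and nearly vanish for near-universal events. The limit on reading the third dose holds whatever the rates and whether or not placebo is pooled.

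**What to change.** Keep the pooled cumulative tables. Footnote them with last follow-up day, placebo numbers by schedule, and scheduled postbaseline draws for hematology, chemistry and coagulation (7/10/14; not urinalysis).

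In SAP 7.1.7 add one table per population of TEAEs (any, related, Grade ≥2, Grade ≥3) with onset within 7 days of each injection:

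- The window matches the diary period (Protocol 6.3.4) and closes before the shortest gap that the visit windows allow, 22 days (Day 32 to Day 54).
- Rows are by injection number, labelled with vector and planned day. Each injection is placed by its actual date, so delayed doses fit.
- The denominator is participants who received that injection, with the same layout for placebo. Planned placebo numbers for injections 1 to 6 are 10/10/6/6/2/2 in Phase 1a (the second falls on Day 29 for 6 and Day 57 for 4) and 6/6/6/6/2/2 in Phase 1b.
- Show beside each row the number not dosed and why. Footnote events whose incomplete start date cannot be placed.
- If a total row of events per injection given is kept, note that it removes the schedule gap only if risk is constant across injections.

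Optional additions in the same layout: treatment-emergent graded blood-test abnormalities at the scheduled draw 14 days after each injection (Days 15, 43, 71, 99, 127, 155; not urinalysis), and solicited diary reactions if the diary data reach the database.

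The cost is SAP wording and two tables from adverse-event and dosing data already collected; the options add up to four. State the downsides:

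- Cells are small. The exact 95% upper limit for 0 events, 1 − 0.025^(1/n), is 37% at n = 8 and 84% at n = 2, so placebo on Days 113 and 141 cannot inform the third dose.
- Events after day 7 remain only in the cumulative tables.
- Participants reaching later injections may be a more tolerant subset, because Protocol 3.3.1 stops dosing after certain related Grade 3 or higher events.
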